## 6.6. Packaging and Labeling

The contents of the label for GSK3196165 will be in accordance with all applicable regulatory requirements for clinical supplies.

## 6.7. Preparation/Handling/Storage/Accountability

No special preparation of study treatment is required.

- Only subjects enrolled in the study may receive study treatment and only the unblinded administrator (study co-ordinator or nurse) may administer study treatment. All study treatments must be stored in a secure environmentally controlled and monitored (manual or automated) area in accordance with the labelled storage conditions with access limited to the investigator and authorized site staff.
- The investigator, institution, or the head of the medical institution (where applicable) is responsible for study treatment accountability, reconciliation, and record maintenance (*i.e.* receipt, reconciliation and final disposition records).

- Further guidance and information for final disposition of unused study treatment are provided in the SRM.
- Under normal conditions of handling and administration, study treatment is not expected to pose significant safety risks to site staff. Take adequate precautions to avoid direct eye or skin contact and the generation of aerosols or mists. In the case of unintentional occupational exposure notify the Medical Monitor and/or GSK study contact.
- A Material Safety Data Sheet (MSDS)/equivalent document describing occupational hazards and recommended handling precautions either will be provided to the investigator, where this is required by local laws, or is available upon request from GSK.

## **6.8. Compliance with Study Treatment Administration**

GSK3196165 or placebo will be administered by subcutaneous injection to subjects at the site by the unblinded administrator (study co-ordinator or nurse). The date and time of each dose and volume administered in the clinic will be recorded in the eCRF.

Subjects will be given instructions on compliance and treatment with MTX. The date taken and total weekly dose will be recorded in the eCRF.

Folic (or folinic) acid must also be taken as instructed in Section [6.1](#).

## **6.9. Treatment of Study Treatment Overdose**

### **6.9.1. Overdose of GSK3196165**

There is very limited clinical safety data at this stage of development. However there have been no reports of overdose with GSK3196165 to date. The risk of overdose occurring is considered low because in GSK3196165 will be administered by an independent administrator, and the maximum volume that can be withdrawn from the vial is equivalent to the highest dose to be evaluated. No specific treatment is recommended for an overdose of GSK3196165, and the investigator should treat as clinically indicated. Details (amount of investigational product given and any resulting AEs/SAEs) should be recorded in the eCRF.

In the event of an overdose the investigator should:

- contact the Medical Monitor immediately
- closely monitor the subject for AEs/SAEs and laboratory abnormalities
- obtain a plasma sample for PK analysis at the time of the event, and three days after the event (unless otherwise requested by the Medical Monitor)
- consult with the Medical Monitor for any decisions regarding dose interruptions or modifications based on the clinical evaluation of the subject.

### **6.9.2. Overdose of Methotrexate**

Refer to the local prescribing information for advice on treatment of MTX overdose. Some guidance is provided below.

Cases of overdose, sometimes fatal, due to erroneous daily intake instead of weekly intake of oral MTX have been reported. In these cases, symptoms that have been commonly reported are hematological and gastrointestinal reactions. Folinic acid is a specific antidote for MTX and, following accidental overdosage, should be administered within one hour at a dosage equal to, or greater than, the MTX dose. It may be administered by IV bolus or infusion. Further doses may be required. The subject should be observed carefully and blood transfusions, renal dialysis and reverse barrier nursing may be necessary. In cases of massive overdose, hydration and urinary alkalisation may be necessary to prevent precipitation of MTX and/or its metabolites in the renal tubules. Neither hemodialysis nor peritoneal dialysis has been shown to improve MTX elimination. Effective clearance of MTX has been reported with acute, intermittent hemodialysis using a high flux dialyser.

### **6.10. Treatment after the End of the Study**

The investigator is responsible for ensuring that consideration has been given to the post-study care of the subject's medical condition, whether or not GSK is providing specific post-study treatment.

### **6.11. Concomitant Medications and Non-Drug Therapies**

During the past decade, the ability of pro-inflammatory cytokines to alter the expression and activity of drug metabolising enzymes has become increasingly evident [Lee, 2010; Zhou, 2011; Evers, 2013]. During inflammation, enzymes such as CYP450 can be down-regulated leading to instances of reduced clearance and increased plasma concentrations of administered drugs. The administration of GSK3196165 can potentially alter circulating cytokine levels to a patient whose cytokine levels have been elevated. This may partially or completely reverse the impact of cytokines on CYP450 enzymes leading to changes in the exposure of co-administered drugs whose metabolism is dependent on CYP450 enzymes. The reports so far suggest the magnitude of drug interaction by therapeutic proteins (clinically) is generally small (less than two-fold) and therefore only likely to be clinically relevant for CYP450 substrates with a narrow therapeutic index, where the dose is individually adjusted. Upon initiation or discontinuation of GSK3196165, in subjects being treated with these types of medicinal products, therapeutic monitoring of effect (e.g., warfarin) or drug concentration (e.g. theophylline) should be performed and the individual dose of the medicinal product adjusted as needed. Prescribers should exercise caution when GSK3196165 is co administered with CYP3A4 substrate drugs where decrease in effectiveness is undesirable, e.g., oral contraceptives, lovastatin, atorvastatin, etc. The effect of GSK3196165 on CYP450 enzyme activity may persist for several weeks after stopping therapy.

## **6.11.1. Permitted Medications and Non-Drug Therapies**

All permitted medications and non-drug therapies will be recorded as concomitant medications.

### **6.11.1.1. Corticosteroids**

#### **6.11.1.1.1. Oral Corticosteroids**

Stable use of oral corticosteroids  $\leq$ 10 mg/day prednisone or equivalent agent is permitted if the dose is stable for at least 28 days prior to Day 1 (baseline). This dose should remain constant throughout the first 12 weeks of the study. Dose reductions before Week 12 are not permitted, unless required for safety or tolerability.

If the corticosteroid dose is increased above 10 mg/day prednisone, the subject will be deemed a treatment failure and investigational product will be discontinued, although the subject will remain on study and undergo study visits as outlined in the Time and Event Table Section 7.1.

#### **6.11.1.1.2. NSAIDS**

Continued use of single NSAID (including Cox-2 inhibitors) is permitted (*i.e.* diclofenac, ibuprofen, naproxen, celecoxib) in daily doses up to the maximum recommended dose, according to locally accepted clinical practices, if the dosage was stable for at least 14 days prior Day 1. The dose/type of NSAID may be changed for safety or tolerability problems. If the subject is not regularly using NSAIDs, he/she may take the NSAIDs mentioned above as breakthrough pain management, which must be recorded in the eCRF. However, subjects should be advised not to take any NSAIDs for breakthrough pain within 12 hours prior to an efficacy assessment visit.

#### **6.11.1.2. Analgesics**

Regular use of codeine, opium alkaloid, paracetamol/acetaminophen, propoxyphene, and tramadol are permitted in daily doses up to the maximum recommended according to locally accepted clinical practices. If the subject is not regularly using any analgesics, he/she may take the analgesics mentioned above as breakthrough pain management. However, the subjects should be advised not to take any analgesics for breakthrough pain within 12 hours prior to an efficacy assessment visit.

## **6.11.2. DMARD/Biologic Rescue Medications**

The subject's disease will be assessed regularly throughout the study (as shown in Section 7.1). Subjects (other than those on the 180 mg dose) will be escalated to the 180 mg (or highest remaining) dose of GSK3196165 at Week 12 if they fail to achieve a EULAR good/moderate response, or at Week 24 if their DAS28(CRP) score is above 3.2. Every effort should be made to keep the subject on study treatment unless the subject experiences an excessive disease flare that, in the investigator's opinion, warrants a change in therapy.

### **6.11.3. Prohibited Medications and Non-Drug Therapies**

#### **6.11.3.1. Related to the Study**

- Any conventional DMARDs other than MTX (including hydroxychloroquine, leflunomide, sulphasalazine, minocycline, ciclosporin, azathioprine).
- Any biologic agent (such as TNF inhibitors such as adalimumab, etanercept, infliximab, certolizumab pegol, golimumab or non-TNF inhibitors (including abatacept, rituximab, tocilizumab and belimumab) and any anti-rheumatic investigational compounds.
- IA corticosteroids are strongly discouraged within 8 weeks prior to Day 1, and then through Week 52.
  - However, IA corticosteroids may be used in a limited fashion as treatment for severe RA flares.
  - No more than 1 joint per 24-week period or 2 joints per 52-week period should be injected.
  - No single injection should exceed 40 mg of triamcinolone (or equivalent) and the total dose of IA corticosteroid should not exceed 80 mg of triamcinolone (or equivalent) during the 52-week period.
- IV and/or IM steroids are not permitted for at least 28 days prior to Day 1, or throughout the study.
- Live vaccines should not be administered for 12 weeks after the last dose of GSK3196165. Furthermore, GSK3196165 and MTX are immunosuppressive and may therefore reduce immunological response to concurrent vaccination. In addition, investigators are expected to assess vaccination status, including against influenza and pneumococcus according to local guidelines.

#### **6.11.3.2. Related to Methotrexate**

Refer to local prescribing information for warnings, precautions and contraindications with MTX treatment.

- Prohibited:
  - Concomitant administration of folate antagonists such as trimethoprim, cotrimoxazole and nitrous oxide are prohibited.
  - Vitamin preparations containing folic acid or its derivatives may alter response to MTX (although folic acid is recommended to reduce the side-effects of MTX, it must not be administered on the same day as MTX)
- Caution advised with the following:
  - MTX is extensively protein bound and may displace, or be displaced by, other acidic drugs. The concurrent administration of agents such as p-aminobenzoic acid, chloramphenicol, penicillins, ciprofloxacin, diphenylhydantoins, phenytoin, acidic anti-inflammatory agents, salicylates,

sulphonamides, tetracyclines, thiazide diuretics, probenicid or sulfinpyrazone or oral hypoglycemics will decrease the MTX transport function of renal tubules, thereby reducing excretion and may increase MTX toxicity.

- MTX may also interact with mercaptopurine and theophylline. Acitretin (a treatment for psoriasis) is metabolised to eretinate. MTX levels may be increased by eretinate and severe hepatitis has been reported following concomitant use.
- Concomitant use of aspirin or NSAIDs
- Hepatotoxic and nephrotoxic drugs.

#### **6.11.3.3. Complementary Therapies**

The use of complementary therapies that may affect RA disease activity or assessments, including, but not limited to, traditional medicine (*e.g.* Chinese, acupuncture, Ayurvedic) is prohibited.

### **7. STUDY ASSESSMENTS AND PROCEDURES**

Protocol waivers or exemptions are not allowed with the exception of immediate safety concerns. Therefore, adherence to the study design requirements, including those specified in the Time and Events Table, are essential and required for study conduct.

This section lists the procedures and parameters of each planned study assessment. The exact timing of each assessment is listed in the Time and Events Table (Section [7.1](#)).

## 7.1. Time and Events Table (Combination Treatment with GSK3196165 and MTX)

Procedures	Screening - up to 4 weeks	Baseline	Treatment Period																												FU 1	EW 1		
			Week																															
			1	2	3	4	6	8	10	12	14	16	18	20	22	24	26	28	30	32	34	36	38	40	42	44	46	48	50	52				
	Visit		Visit																															
	1	2	3	4	5	6	7	8	9	10	11	12	13	14	15	16	17	18	19	20	21	22	23	24	25	26	27	28	29	30	31	32		
	Day	Day	Day 																															
	-7	1	3*	8	15	22	29	43	57	71	85	99	113	127	141	155	169	183	197	211	225	239	253	267	281	295	309	323	337	351	365	435		
Written Informed Consent(s)	X																																	
Subject Demography	X																																	
Medical, Disease, Therapy History	X																																	
Inclusion/Exclusion Criteria	X																																	
Efficacy and PRO Assessments																																		
Swollen (66) & Tender (68) Joint Count 	X	X 	X	X	X	X	X	X	X	X	X	X	X	X	X	X	X	X	X	X	X	X	X	X	X	X	X	X	X	X				
Patient's Assessment of Arthritis Pain, Patient's Global Assessment of Arthritis, Physician's Global Assessment of Arthritis 	X	X 	X	X	X	X	X	X	X	X	X	X	X	X	X	X	X	X	X	X	X	X	X	X	X	X	X	X	X	X				
HAQ-DI 	X	X 	X	X	X	X	X	X	X	X	X	X	X	X	X	X	X	X	X	X	X	X	X	X	X	X	X	X	X	X				
BFI Question 3, FACIT-Fatigue, SF-36 (acute v2) 		X 				X																										X	X	X
RA Symptom and Impact Diary 		X 	X																													X	X	
RA Symptom and Impact Diary, Actigraphy process 		X 		X 																												X 	X 	X 

Procedures	Screening - up to 4 weeks	Baseline	Treatment Period																											FU	EW 1					
			Week																																	
			1	2	3	4	6	8	10	12	14	16	18	20	22	24	26	28	30	32	34	36	38	40	42	44	46	48	50	52						
	Visit	Visit	1	2	3	4	5	6	7	8	9	10	11	12	13	14	15	16	17	18	19	20	21	22	23	24	25	26	27	28	29	30	31	32		
			Day	Day																																
	-7	1	3*	8	15	22	29	43	57	71	85	99	113	127	141	155	169	183	197	211	225	239	253	267	281	295	309	323	337	351	365	435				
Safety Evaluations																																				
Concomitant Medication	X		X 	Record all concomitant medications																																
Physical Examination  , Vital Signs	X 		X		X	X		X		X		X		X		X		X		X		X		X		X		X		X	X	X				
12-lead ECG 	X																																X	X		
AEs/SAEs/AESI	X		X	X	X	X	X	X	X	X	X	X	X	X	X	X	X	X	X	X	X	X	X	X	X	X	X	X	X	X	X					
Cough, Lung Auscultation, Pulse Oximetry, Borg Dyspnea Scale	X		X 		X	X	X	X	X	X	X	X	X	X	X	X	X	X	X	X	X	X	X	X	X	X	X	X	X	X	X					
Chest X-ray 	X																																			
Spirometry (FEV1, FVC)	X		X 																													X	X	X		
D LCO	X 		X 																														X	X	X	
Laboratory Assessments																																				
Hematology, Chemistry	X		X 			X		X		X		X		X		X		X		X		X		X		X		X		X	X	X				
Urinalysis (dip stick)	X																																X	X	X	
Cholesterol, triglycerides, HDL, LDL 			X 																															X	X	X
Pregnancy test 	S		U																																	
TB, HBsAg, Hep B cAb, HepC Ab, HIV	X																																			
RF, ACPA (anti-CCP)	X																																			
CRP, ESR 	X		X 		X	X		X	X	X		X		X		X		X		X		X		X		X		X		X	X	X				
Other Laboratory Assessments																																				
PK Sampling (GSK3196165) 			X 	X*	X	X		X	X	X		X		X		X		X		X		X		X		X		X		X	X	X				

Procedures	Screening - up to 4 weeks	Baseline	Treatment Period																												FU	EW 1					
			Week																																		
			1	2	3	4	6	8	10	12	14	16	18	20	22	24	26	28	30	32	34	36	38	40	42	44	46	48	50	52	62						
	Visit		Visit																																		
	1	2	3	4	5	6	7	8	9	10	11	12	13	14	15	16	17	18	19	20	21	22	23	24	25	26	27	28	29	30	31	32					
	Day	Day	Day 																																		
	-7	1	3*	8	15	22	29	43	57	71	85	99	113	127	141	155	169	183	197	211	225	239	253	267	281	295	309	323	337	351	365	435					
GM-CSF & PD blood biomarkers		X 	X*	X	X		X		X									X															X	X	X		
PGx sampling RNA 		X 									X								X														X	X	X		
PGx sampling DNA 		X 																																			
Lung biomarkers 		X 									X								X														X	X	X		
Cholesterol/4β-hydroxycholesterol		X 									X																										
Immunoogenicity 		X 			X		X			X								X															X	X	X		
Anti-GM-CSF auto-antibodies 		X 																																			
Study Treatment GSK3196165/placebo (Methotrexate and folic acid weekly throughout treatment with GSK3196165)		X	X	X	X	X	X	X	X	X	X	X	X	X	X	X	X	X	X	X	X	X	X	X	X	X	X	X	X	X	X	X	X				
Rescue point for possible dose escalation											X								X																		
Decision point for mandated withdrawal 																																					

1. All subjects who discontinue study medication prematurely should have an early withdrawal (EW) visit as soon as possible after study agent discontinuation and then return for a follow-up safety visit at least 12 weeks after last dose of study medication.
2. The same individual (where possible) should perform all disease assessments for an individual subject (with separate joint assessor).
3. All PRO assessments should be conducted before any tests, procedures, assessments or consultations, to avoid influencing the subjects' perception.
4. Assessments may be performed up to 24 hours before dosing GSK3196165.
5. Non-actigraphy sub-study subjects only.
6. Performed in a subset of consenting subjects only.
7. Actigraphy device placed and tagging process started (as detailed in the SRM), RA Symptom and Impact Diary questionnaire started on the same day at home using an electronic PRO (ePRO) device and completed on a daily basis until next visit.
8. Actigraphy device collected and RA Symptom and Impact Diary questionnaire completed at site visit and ePRO device collected.
9. All safety evaluations should be conducted before dosing GSK3196165.
10. Complete physical at baseline, and then limited physical examination (abdominal examination and heart sounds) thereafter.
11. ECG should be performed before vital signs, blood draws, and dosing.
12. Unless performed within previous 12 weeks (No need to repeat if subject re-screened).
13. Chest HRCT if  $D_{LCO} \geq 60\% - < 70\%$  predicted (No need to repeat if subject re-screened).
14. If the screening  $D_{LCO}$  value is  $\geq 70\%$  predicted, but the subsequent "Day 1" value is  $< 70$  but  $\geq 60\%$  predicted, the  $D_{LCO}$  test must be repeated if still within the screening window. If the repeat value is  $\geq 70\%$ , the "Day 1" activities may be completed, but if the value is again  $< 70\%$ , dosing must be postponed and a chest HRCT performed. If this cannot be done within the screening window then the subject must be re-screened.
15.  $>8h$  fasting required before blood draw.
16. For women of child-bearing potential. S=serum; U=urine.
17. ESR measured locally.
18. Blood samples taken before dosing GSK3196165.
19. In consenting subjects.
20. To be analysed at end of study or in event of pulmonary safety signal.
21. In addition to these scheduled immunogenicity assessments, "event-driven" testing (see Section 7.6) will also be employed for those subjects that experience anaphylaxis, serious hypersensitivity, or adverse events related to study drug administration that led to withdrawal from the study.
22. GSK3196165 or placebo must be administered on the same day each week  $\pm 1$  day for the first 5 weekly doses, thereafter on the same day EOW  $\pm 3$  days.
23. Any subject not achieving EULAR good/moderate response at Week 36 will be withdrawn from the study at Week 38.

\* The Day 3 blood sample may be drawn  $\pm 1$  day.

## 7.2. Screening and Critical Baseline Assessments

After written, informed consent (including separate consent for genetics research and actigraphy sub-study at participating sites), screening assessments will be performed. Screening procedures are outlined in the Time and Events Table (Section 7.1). All screening assessments must be performed within 28 days of Day 1 (except for subjects being treated with azathioprine or leflunomide, where written informed consent for the study, or sub-study, must be obtained prior to beginning the screening period). Women and men of reproductive potential must consent to use of a highly effective method of contraception for the duration of the study and for 12 weeks after study end (see [Appendix 12.2](#)), and the method (s) used by each subject must be documented.

- The following demographic parameters will be captured: year of birth, sex, race and ethnicity.
- Medical/medication/family history will be assessed as related to the inclusion/exclusion criteria listed in Section 5.
- Cardiovascular medical history/risk factors (as detailed in the eCRF) will be assessed at screening.
- Rheumatoid arthritis history – disease duration, medication history, RA functional class (I, II or III).
- Physical examination (complete examination at screening, and brief examination at Day 1 visit; see Section 7.4.8).
- Vital signs including temperature, sitting blood pressure, and heart rate.
- TriPLICATE 12-lead ECG (before blood samples are taken).
  - Spirometry FEV1, FVC and DLCO (see SRM for additional details).
- Blood samples for:
  - Hematology (full/complete blood count and differential), including ESR (screening and baseline).
  - Biochemistry (screening and baseline).
  - Serum βhCG pregnancy test (screening).
  - HIV antibody, Hepatitis B surface antigen, anti-HBc, and Hepatitis C antibody testing (screening).
  - CRP (screening and baseline).
  - Autoimmune serology: RF and ACPA (*i.e.*, anti-CCP antibodies) (screening).
  - QuantiFERON Gold or T-spot test for TB (If unavailable/unapproved, then tuberculin skin test is permitted). TB tests may be performed locally.
  - Exploratory GM-CSF, PD and lung biomarkers (baseline).
  - Plasma PK samples and immunogenicity (baseline).
  - Pharmacogenomic and RNA transcriptomic tests (in consenting subjects).

- Urine sample for:
  - Routine urinalysis (screening).
  - Urine  $\beta$ hCG pregnancy test (baseline).
- Disease activity assessments (screening and baseline) (see Section 7.3)
  - Tender joint count (68 joints).
  - Swollen joint count (66 joints).
  - Patient's Assessment of Arthritis Pain.
  - Patient's Global Assessment of Arthritis.
  - Physician's Global Assessment of Arthritis.
  - HAQ-DI.
- Patient-reported outcome questionnaires (baseline) (see Section 7.10)
  - Component of BFI.
  - FACIT-Fatigue.
  - Acute SF-36.
  - RA Symptom and Impact Diary.
  - Actigraphy (in consenting subjects at participating sites).

Patient-reported outcomes questionnaires should be completed by subjects before any other assessment at a clinic visit, in the order specified in the SRM.

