### 4.6.1. Dose Recommendation

An eight-fold range of doses, that are expected to result in largely non-overlapping exposures, as well as placebo, are proposed for evaluation: placebo, 22.5 mg, 45 mg, 90 mg, 135 mg and 180 mg, with corresponding volumes of 0.15, 0.3, 0.6, 0.9, and 1.2 mL, respectively, which allow for ease of administration with standard syringes. Study agent will be administered SC weekly for 5 injections (Days 1, 8, 15, 22, 29), then EOW thereafter beginning at Day 43 (Week 6) and ending at Day 351 (Week 50). The doses of GSK3196165 have been selected based upon the results from previously conducted studies of the molecule.

A wide range of doses is being studied in order to fully characterise the dose response (Figure 1). The dose range includes doses that are anticipated to be effective or minimally effective based on the Phase 1b/2a RA study where IV doses of 1.0 mg/kg and 1.5 mg/kg showed activity and 0.3 mg/kg showed little to no activity after 4 weeks of treatment (see IB GSK Document Number [2014N190256\_01]). Furthermore, doses of 90, 135, and 180 mg SC given every other week (EOW) are anticipated to result in steady state  $C_{min}$  concentration levels of approximately 2 µg/mL or greater (a hypothetical target to bind synovial GM-CSF based on in vitro data, and early clinical data, see IB GSK Document Number [2014N190256\_01]). The weekly loading dose regimen is intended to achieve rapid reduction in disease activity, as supported by the completed 4 week RA study (MSC1001) where doses of 1.0 and 1.5 mg/kg IV weekly were associated with reduction of DAS28 score after the first dose that continued to decrease through Week 3 and 6, respectively (see IB GSK Document Number [2014N190256\_01]).

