## 5.6. Subject and Study Completion

A completed subject is one who has completed all phases of the study including the follow-up visit.

The end of the study is defined as the last subject's last visit.

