## **10.8. Review Committees**

### **10.8.1. Data Review Committee (DRC)**

- A DRC will be utilised in this study to ensure objective medical and/or statistical review of efficacy and/or safety issues in order to protect the ethical and safety interests of subjects and to protect the scientific validity of the study via review of unblinded study data.
- The DRC (consisting of external rheumatology, infectious disease and respiratory experts, and GSK study team members that have no involvement in the acquisition of the data or direct contact with sites) will review ongoing unblinded safety data from the study and unblinded efficacy data at the interim analyses. The first DRC review of safety data will be conducted after approximately 10 subjects per arm have completed 5 weeks of treatment, and subsequent reviews will take place

approximately every 12 weeks thereafter until the end of the study. The decision to stop the study or randomisation to specific arms will be made by the DRC.

- The DRC members will review unblinded summary safety data, and if required will review anonymised individual data on request. Only the DRC statistician will be unblinded to individual subject treatment allocations.
- At the defined interim analysis time points the DRC will also review unblinded efficacy data. Unblinded efficacy data will also be reviewed if needed outside of the planned interim analyses to assess benefit:risk based on the safety findings. When possible, these reviews will be scheduled to align with planned safety reviews. The schedule of planned interim analyses and the analysis plan for DRC reviews will be described in the relevant guidance documents that will be approved prior to the first analysis, which will be available upon request.
- The DRC will remain in place for review of emerging unblinded safety data until all subjects have completed the safety follow-up visit (*i.e.*, 12 weeks after the last dose of study medication, Week 62 visit). The Week 24 efficacy and safety analyses (primary analysis) will be made available to the study team more broadly and to regulatory authorities as these data will support future clinical development plans.
- A vote of the DRC committee will be taken at the conclusion of each meeting of the DRC. Each meeting of the committee will be associated with an active recommendation of proceeding unchanged, modifying or terminating the study. Further details will be outlined in the DRC Charter.

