## 12.2. Appendix 12.2 - Contraception eligibility criteria for female and male subjects

### 12.2.1. Females

A female subject is eligible to participate if she is not pregnant (as confirmed by a negative serum human chorionic gonadotropin [ $\beta$ hCG] test), not lactating, and at least one of the following conditions applies:

a. Non-reproductive potential defined as:

- Pre-menopausal females with one of the following:
  - Documented tubal ligation.
  - Documented hysteroscopic tubal occlusion procedure with follow-up confirmation of bilateral tubal occlusion.
  - Hysterectomy.
  - Documented bilateral oophorectomy.
- Postmenopausal defined as 12 months of spontaneous amenorrhea [in questionable cases a blood sample with simultaneous follicle-stimulating hormone (FSH) and estradiol levels consistent with menopause (refer to laboratory reference ranges for confirmatory levels)]. Females on hormone replacement therapy (HRT) and whose menopausal status is in doubt will be required to use one of the highly effective contraception methods if they wish to continue their HRT during the study. Otherwise, they must discontinue HRT to allow confirmation of post-menopausal status prior to study enrolment.

b. Reproductive potential and agrees to follow one of the options listed below in the **Modified List of Highly Effective Methods for Avoiding Pregnancy in Females of Reproductive Potential (FRP)** requirements from 30 days prior to the first dose of study medication and until 12 weeks after the last dose of study medication and completion of the follow-up visit. **If using hormonal contraceptives, including oral, injections, implants, and patches, a secondary method of contraception must be used.**

The investigator is responsible for ensuring that subjects understand how to properly use these methods of contraception.

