#### **12.2.2. Males**

Male subjects with female partners of child bearing potential must comply with the following contraception requirements from the time of first dose of study medication until 12 weeks after the last dose of study medication.

- a. Vasectomy with documentation of azoospermia. The documentation on male sterility can come from the site personnel's review of subject's medical records, medical examination and/or semen analysis, or medical history interview.
- b. Male condom plus partner use of one of the contraceptive options below:
  - Contraceptive subdermal implant.
  - Intrauterine device or intrauterine system.
  - Combined estrogen and progestogen oral contraceptive [Hatcher, 2011].
  - Injectable progestogen [Hatcher, 2011].
  - Contraceptive vaginal ring [Hatcher, 2011].
  - Percutaneous contraceptive patches [Hatcher, 2011].

These allowed methods of contraception are only effective when used consistently, correctly and in accordance with the product label. The investigator is responsible for ensuring that subjects understand how to properly use these methods of contraception.

Male subjects should not donate sperm during the course of the study and should follow local guidelines thereafter.

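### Contraception end date: protocol section 7.2 counts 12 weeks from study end, the appendix it cites counts from the last dose, and the passages must be reconciled

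*Protocol*

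**What the plan says.** Four parts of the protocol bear on when the contraception requirement ends.

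- **Section 7.2 (screening and baseline).** Women and men of reproductive potential must consent to highly effective contraception "for the duration of the study and for 12 weeks after study end". The sentence points to Appendix 12.2 and does not define study end.
- **Appendix 12.2.1 (females).** The requirement lasts "until 12 weeks after the last dose of study medication and completion of the follow-up visit".
- **Appendix 12.2.2 (males).** The requirement runs "from the time of first dose of study medication until 12 weeks after the last dose of study medication". There is no follow-up clause.
- **Section 5.6.** "The end of the study is defined as the last subject's last visit". The same section says of the individual subject: "A completed subject is one who has completed all phases of the study including the follow-up visit".

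Inclusion criterion 10 in section 5.1 makes agreement to the Appendix 12.2 criteria a condition of entry. It does not cite section 7.2.

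**The concern.** Section 7.2 sends the reader to the appendix for its contraception rule, yet the two start the 12-week count at different events. The appendix counts from the last dose. Section 7.2 counts from study end, which on the section 5.6 definition cannot come before a subject's follow-up visit, and that visit is itself scheduled 12 weeks after the last dose. On that definition section 7.2 only begins its 12 weeks at or after the point where the appendix period for men has run out.

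This is a reproductive-safety obligation. What subjects must consent to (7.2) and what they must agree to for eligibility (criterion 10, through Appendix 12.2) carry different end dates, and section 7.2 does not say which prevails. A site following the appendix could fall short of 7.2. A site following 7.2 could extend the obligation beyond the last scheduled visit and beyond the end of adverse event collection, which section 7.4.4.1 places at the follow-up contact 12 weeks after the last dose. No efficacy endpoint or analysis is affected.

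**Working it through.** **Inputs**

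- Last dose: section 4.6.1 has dosing "ending at Day 351 (Week 50").
- Follow-up visit: section 10.8.1 gives it as "12 weeks after the last dose of study medication, Week 62 visit". The Time and Events Table (7.1) puts it at Day 435.
- Week 52 visit: Day 365 in the same table.
- Week-to-day rule implied by the table: Day = 7 × Week + 1.

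**Reproducing the protocol's own interval.** Day 435 − Day 351 = 84 days = 12 weeks. The schedule agrees with itself.

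**Appendix period for a completer.** Last dose + 84 days = 351 + 84 = Day 435, which is Week 62. This applies directly to men. For women the follow-up clause allows two parses:

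- The later of (last dose + 12 weeks) and the follow-up visit. Both fall at Day 435, so the period ends at about Week 62. This is the natural reading.
- Twelve weeks after both the last dose and the follow-up visit: 435 + 84 = Day 519, Week 74.

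**Section 7.2 period for a completer.** Study end + 84 days, under each meaning that study end could have:

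| Meaning of study end | Section 7.2 period ends | Gap from Week 62 |
|---|---|---|
| Subject's own follow-up visit (Day 435) | 435 + 84 = Day 519, Week 74 | 12 weeks |
| Last subject's last visit (section 5.6), r weeks after the subject's own | Week 74 + r | 12 + r weeks |
| Week 52 visit (Day 365) | 365 + 84 = Day 449, Week 64 | 2 weeks |

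The value of r depends on recruitment, which the documents do not fix. As illustrations only, r = 0 gives 12 weeks, r = 26 gives 38 and r = 52 gives 64.

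**A subject who does not complete.** Take someone who fails the Week 36 response criterion, whose last dose is then at Week 36 (Day 253). The appendix count for a man ends at 253 + 84 = Day 337, Week 48.

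- If study end is the follow-up visit, which a withdrawn subject must still attend at least 12 weeks after the last dose (Day 337 or later), section 7.2 ends no earlier than 337 + 84 = Day 421, Week 60. The gap is at least 12 weeks.
- If study end is the withdrawal at Week 38 (Day 267), section 7.2 ends at 267 + 84 = Day 351, Week 50. The gap is 2 weeks.

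The size of the gap therefore depends on what study end means, for completers and for those withdrawn.

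**The case against.** The strongest reply is that section 7.2 is a screening summary that refers to Appendix 12.2, and that eligibility under criterion 10 rests on the appendix alone. Most sites would probably go to the appendix. That lowers the practical risk, but section 7.2 states a period of its own as something subjects must consent to, and the cross-reference does not make the two periods equal.

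A second reply is that section 5.6 defines the end of the trial, whereas section 7.2 is about what one person agrees to, and a date nobody can know at consent is unlikely to have been intended. This has weight, and it is why the gap cannot be stated without conditions. It does not remove the conflict. SAP section 4.2 defines each subject's end of study, for analysis, as the last available assessment on or after the last treatment day. For a completer who attends follow-up, that is Week 62, and section 7.2 then ends at Week 74. The design schematic shows local standard of care from Week 52, which could suggest that Week 52 was meant, but section 5.6 counts the follow-up visit as part of a subject's completion.

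A third reply is that section 7.2 is the longer rule, so following it satisfies the appendix. Against the male text this holds on each reading above. It need not hold for women: if study end meant Week 52 (period to Week 64) and the female clause were parsed to Week 74, section 7.2 would be the shorter.

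A reader might infer more than the documents support:

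- **That the gap is at least 12 weeks for everyone.** Section 7.2 does not define study end, and the looser readings give 2 weeks.
- **That the male and female texts conflict equally with 7.2.** The female wording can be parsed to agree with 7.2 at subject level, at Week 74.
- **That subjects are actually told two different dates.** The consent pages are not available for review, so this cannot be checked either way.

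**Conclusion.** The inconsistency is real and lies in current protocol text. Section 7.2 and Appendix 12.2.2 count the same 12 weeks from different events, so the conflict for men is unambiguous. For women, section 7.2 conflicts with the natural reading of Appendix 12.2.1, and the clause is unclear enough to need redrafting in any case.

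For a completer the appendix period ends at about Week 62. The section 7.2 period ends at Week 74 if study end is the subject's own last visit. Under section 5.6 it ends at Week 74 or later, with no date the subject could know in advance. The 12-week figure assumes that study end falls no earlier than the subject's follow-up visit, which section 5.6 supports. The 2-week alternative needs study end to mean the Week 52 visit or, for a subject withdrawn under the Week 36 rule, the withdrawal at Week 38.

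This is more than clerical, because it concerns a safety obligation that subjects must consent to, but it is modest in consequence. Nothing here shows which period is right.

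**What to change.** Reconcile section 7.2, Appendix 12.2.1 and Appendix 12.2.2 to one end point, expressed from an event whose date each subject can identify. The sponsor must decide which period applies. Two points of drafting follow:

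- Either define study end where section 7.2 uses it, or remove the separate period from 7.2 and rely on the appendix.
- Reword the female clause so that it is clear whether the 12 weeks run from the last dose only or also from the follow-up visit, and say whether any difference between women and men is intended.

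Then check that the consent form states the same period. The cost is protocol wording, plus consent wording only if that check finds a mismatch. No assessment, sample size or analysis changes.
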